#### **Adverse Events**

Adverse events will be coded using the most recent version of the MedDRA that will have been released for execution at AstraZeneca. AEs will be presented for each treatment group by SOC and/or Preferred Term covering number and percentage of participants reporting at least one event and number of events where appropriate. Exposure-adjusted incidence rates may be provided as appropriate. Only treatment-emergent AEs will be summarized.

An overview of AEs will present the number and percentage of participants with any AE, AEs with outcome of death, serious AEs, AEs leading to discontinuation of IP, and AEs leading to dose reduction of IP for each treatment group.

Separate AE tables will be provided taking into consideration the relationship as assessed by the investigator, maximum intensity, seriousness, death and events leading to discontinuation of IP as well as AESIs.

In accordance with the requirements of the FDA, a separate table will present non-serious AEs occurring in more than 5% of participants in any treatment group.

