#### **Adverse Event Variables**

'The following variables will be collected for each AE:

- AE (verbatim)
- The date when the AE started and stopped
- Maximum intensity
- Whether the AE is serious or not
- Investigator causality rating against the IP(s) (yes or no)
- Investigator causality rating against the study procedure(s) (yes or no)
- Action taken with regard to IP(s)
- AE caused participant's withdrawal from study (yes or no)
- Outcome

In addition, the following variables will be collected for SAEs:

- Date AE met criteria for SAE
- Date investigator became aware of SAE
- AE is serious due to
- Date of hospitalization
- Date of discharge
- Probable cause of death
- Date of death
- Autopsy performed
- Causality assessment to other medication

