# **Appendix B** Adverse Events: Definitions and Procedures for Recording, Evaluating, Follow-up, and Reporting

#### **B 1** Definition of Adverse Events

An AE is the development of any untoward medical occurrence in a patient or clinical study participant administered a medicinal product and which does not necessarily have a causal relationship with this treatment. An AE can therefore be any unfavorable and unintended sign (eg, an abnormal laboratory finding), symptom (for example nausea, chest pain), or disease temporally associated with the use of a medicinal product, whether or not considered related to the medicinal product.

The term AE is used to include both serious and non-serious AEs and can include a deterioration of a pre-existing medical occurrence. An AE may occur at any time, including run-in or washout periods, even if no study intervention has been administered.

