# 3.3.1.2 Definition of On-study and On-treatment

All adverse events (AEs) with start date on or after the date of first treatment will be considered on-study. On-treatment AEs are those occurring within the on-study period and within + 7 days of treatment discontinuation. All AEs leading to discontinuation of IP will be considered on-treatment.

On-study assessments (eg, vital signs, clinical laboratory tests, ECG) are defined as those occurring after the date and time (if available) of administration of the first dose of IP. On-

treatment assessments are defined as those occurring within the on-study period and on or before the date of administration of the last dose of IP with the following windows following treatment discontinuation:

- Fasting plasma glucose (FPG): +1 day from treatment discontinuation.
- Biopsy, liver tests (alanine aminotransferase [ALT], aspartate aminotransferase [AST], total bilirubin [TBL], and alkaline phosphatase [ALP]), and disease-specific biomarkers: + 30 days from treatment discontinuation.
- All other efficacy and safety: +7 days from treatment discontinuation.

Assessments other than AEs recorded on the day of first treatment and with time unavailable for the assessment or for the first dose, will be considered to be not in the on-study/on-treatment periods. For listings of AEs, analysis phase will be indicated as on-treatment if the AE starts within the on-treatment period, as 'pre-treatment' if it starts prior to the on-treatment period, and as 'post-treatment' if it starts after the on-treatment period.

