#### 4.5.2.2 Presentation

AEs will be summarized for each treatment group. The AE tables will be based on the safety analysis set. Summary tables will include all on-study AEs. Select AE and AESI summaries will be repeated for all on-treatment events as appropriate.

Summary tables are listed below.

An overview table will contain summaries of the number and percentage of participants with the following:

- Any AE
- Any AE considered related to IP
- Any AE leading to death
- Any SAE
- Any AE leading to discontinuation of IP

- Any AE leading to a reduction of IP dose
- Any AE leading to withdrawal from the study

The following summary tables will be presented by SOC and PT:

- Any AE
- Any AE considered related to IP
- Any AE leading to death
- Any SAE
- Any AE leading to discontinuation of IP
- Any AE leading to a reduction of IP dose
- Any AE leading to withdrawal from the study
- The number and percentage of participants with any AEs by maximum reported intensity

On-study AESIs will be summarized as number and percentage of participants with the following:

- Any AESI
- Each specific AESI will also be summarized, overall and by maximum intensity
- Each specific AESI will be summarized by SOC and PT
- Select AESI summaries will be repeated for all on-treatment events as appropriate

Adjudicated events (separate on-study and on-treatment analyses) will be summarized as number and percentage of participants with the following:

- Any liver event (hepatic decompensation, clinical cirrhosis, DILI, hepatocellular carcinoma, or death from any cause)
- Events of hepatic decompensation
  - Clinically apparent ascites requiring treatment
  - Complication of ascites (eg, spontaneous bacterial peritonitis, diuretic-resistant ascites [refractory ascites], hepato-pleural effusion)
  - Hepatic encephalopathy of Grade 2 or above (according to the West Haven criteria) requiring treatment
  - Portal hypertension-related upper gastrointestinal bleeding identified by endoscopy and requiring hospitalization, including events of bleeding from esophageal varices, gastric varices, and portal hypertensive gastropathy
- Clinical cirrhosis
- DILI
- Hepatocellular carcinoma

- Death by any cause
- 3-point MACE
- 5-point MACE
- CV death
- Cardiac ischemic events Myocardial Infarction (non-fatal)
- Cardiac ischemic events Myocardial Infarction (any)
- Cerebrovascular events- Stroke (non-fatal)
- Cerebrovascular events- Stroke (any)

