- Cardiac ischemic events- Hospitalization for Unstable Angina
- Hospitalization for heart failure
- Diabetic ketoacidosis
- Thyroid carcinoma
- Pancreatitis
- Pancreatic carcinoma

Additional analyses will be provided for adjudicated events, if required.

Where number of participants with AEs are summarized by SOC and PT, participants with multiple events in the same SOC/PT are counted only once in that SOC/PT. Participants with events in more than 1 SOC/PT are counted once in each of those SOCs/PTs. Participants with multiple occurrences of the same AESI will be counted once at the maximum observed severity. Tables will be sorted by international order for SOC and in alphabetical order for PT.

Additionally, the following tables will be presented:

• The number and percentage of participants with non-serious AEs occurring with a frequency > 5.0% in any treatment group for each SOC and PT. This table will be produced as a separate pdf output to meet clinical trial transparency requirements and not for inclusion in the CSR.

A list of key participant information for participants with AEs with outcome of death, participants with SAEs, and participants with AEs leading to discontinuation of IP will be provided. The durations reported in these tables will be derived only for fully completed dates as below:

• Time from first dose of IP to AE (in days) will be calculated as the AE start date minus date of dose +1.

- Time from first dose to death (in days) will be calculated as the date of death minus date of dose +1.
- The same approach will be used for deriving time from start of treatment to AE becoming serious or discontinuation.
- Time from last dose prior to AE start and last dose prior to death will be calculated as the date of death minus the date of last dose prior to AE/death +1.

All AEs will be listed (including AEs before the date of first dose).

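### SAP 3.3.1.2 classes AEs as on-study by start date, so a screening-onset AE that becomes serious or leads to dose reduction after first dose is missing from the AE summary tables

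*Protocol*

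**What the plan says.** Protocol 9.4.3 (Adverse Events) limits the tables: "Only treatment-emergent AEs will be summarized". The protocol does not define the term for AEs. SAP 3.3.1.2 gives the operative rule: "All adverse events (AEs) with start date on or after the date of first treatment will be considered on-study". SAP 4.5.2.2 then applies it: "Summary tables will include all on-study AEs".

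The same SAP section nests on-treatment AEs inside the on-study period, up to 7 days after treatment discontinuation, and then adds: "All AEs leading to discontinuation of IP will be considered on-treatment".

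Deaths and certain other events have a second route: "Adjudicated events (separate on-study and on-treatment analyses) will be summarized as number and percentage of participants with the following". That summary has rows for death by any cause, MACE and liver events, among others. Protocol 8.3.10 sends all deaths to adjudication.

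The AE variables in protocol 8.3.2 are one start date, one stop date and one maximum intensity. For SAEs there is a separate field, "Date AE met criteria for SAE". The SAP uses such a date in its key-information lists, where it derives "time from start of treatment to AE becoming serious or discontinuation".

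**The concern.** AEs are collected from consent. Screening can last up to 56 days and may include a liver biopsy, whose complications are reportable as AEs (protocol 8.3.7). Some participants may therefore have an AE open at first dose. If that AE later becomes serious or dose-limiting on study drug, the clinically important part of the event falls after dosing, but the start date does not. The SAP expects onset and seriousness to differ, since it derives a time to becoming serious. It does not use that date to decide which table an event belongs in.

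The AE rule is also stricter than its neighbours. For laboratory, vital-sign and ECG abnormalities, SAP 4.5 counts a result as treatment-emergent when it is more extreme than baseline. Under SAP 3.3.1.4.2, an AE with a missing start day in the month of first dose, and not ended before that dose, is given the first-dose date and so becomes on-study. The same AE with a known pre-dose date is excluded.

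At stake is whether the SAE and dose-reduction counts, which serve the primary endpoint, include every event that reached that status on treatment.

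**Working it through.** There is no stated figure to reproduce. The check traces an AE that starts before first dose, and is kept as one record, through SAP 3.3.1.2 and 4.5.2.2.

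1. **Becomes serious after dosing, not fatal, not an adjudicated event type, IP continued.** The start date precedes first treatment, so the AE is not on-study. It is absent from the overview and from the SOC/PT tables, including SAEs and maximum intensity, and from the AESI tables if it is an AESI. It stays in the SAE key-information list, which carries no stated on-study restriction, and in the full AE listing, where its analysis phase is pre-treatment.
2. **Leads to IP dose reduction.** By the same rule it is absent from the overview row and the SOC/PT table for dose reduction. It appears in the full AE listing.
3. **Fatal after dosing.** It is absent from the table of AEs leading to death. The death belongs in the adjudicated row for death by any cause and in the MACE and liver-event composites, provided adjudicated events are dated by the event itself. The SAP does not state how they are dated. Two death counts could therefore disagree.
4. **Leads to IP discontinuation.** Three readings are possible. If the discontinuation sentence overrides the start date, the AE is on-treatment but not on-study, and an on-treatment repeat of the table could hold an event that the main table lacks. If the sentence only waives the 7-day limit, the AE is in neither. If being on-treatment implies being on-study, it is in both. The SAP does not choose.
5. **Worsening entered as a new AE record with a post-dose start date.** It is on-study and is tabulated.

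**Scale of one omission.** The inputs are about 55 randomized (protocol 9.2) and the ratio 2:1:2:1 (protocol 6.3.1).

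- Each dose arm, or the two placebo groups pooled: 55 × 2/6 = 18.3; 1/18.3 = 5.5 percentage points.
- A single placebo group: 55 × 1/6 = 9.2; 1/9.2 = 10.9 percentage points.

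How many such AEs to expect cannot be worked out, because the documents give no rate of AEs open at first dose or of later escalation.

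**The case against.** A reader might infer that these events reach no summary table at all, or that start date is the only route in. The documents do not support that. All deaths are adjudicated and summarized, as are myocardial infarction, stroke, hospitalization for heart failure, DILI, pancreatitis, diabetic ketoacidosis and other listed types, and adjudicated events are part of the primary safety endpoint. AEs leading to IP discontinuation have their own sentence. Nothing is lost from the record: all AEs are listed, including those before first dose, and with about 55 participants case-level review is practical.

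A second objection is that protocol Appendix B 1 says an AE "can include a deterioration of a pre-existing medical occurrence", so a post-dose worsening may be entered as a new AE and counted. That is possible. However, neither document requires a new record, and one record with a maximum intensity and a separate seriousness date accommodates escalation without one.

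A reader might also infer a measurable bias between arms. None is shown. Onset precedes randomization, treatment is blinded, the safety analysis is descriptive, and any estimate of the number omitted would rest on assumed rates.

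After these objections, cases 1 and 2 remain, together with the possible mismatch in death counts and the undefined precedence for discontinuation AEs.

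**Conclusion.** The point holds in limited form. As written, the SAP rule gives incomplete counts in the overview, SAE and dose-reduction tables, and in the AESI tables where relevant, for AEs with pre-dose onset that escalate after dosing. It also omits a fatal case from the table of AEs leading to death, even though the death should be counted among adjudicated events. The status of a screening-onset AE that stops IP is ambiguous.

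This rests on the AE being kept as one record, which the documents allow but do not require. The frequency is unknown and may be zero. One such participant is about 5.5 percentage points in an arm of about 18. It should be corrected before unblinding, because the rule affects primary-endpoint tables and the remedy is cheap.

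**What to change.** In SAP 3.3.1.2, define a treatment-emergent (on-study) AE once, as either:

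- an AE starting on or after first dose; or
- an AE with earlier onset and any of: SAE criteria met on or after first dose, fatal outcome, IP discontinuation, or IP dose reduction.

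State that AEs leading to IP discontinuation are both on-study and on-treatment. For the added records, assign the period by the SAE-criteria date, the death date, or the recorded dose-change or stop date. Have protocol 9.4.3 refer to this definition.

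Inclusion needs no new data. The SAE-criteria date, outcome and action taken are collected (protocol 8.3.2), and a death, discontinuation or dose reduction in a treated participant is necessarily after first dose. The cost is wording and minor programming. The one extra step is linking dose-change dates, which protocol 6.4 records apart from the AE, to the AE records. The change does not bring in an AE that only worsens in intensity, since no date of worsening is listed among the AE variables.

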#### Vital Signs

Vital sign parameters will be presented for each treatment group. Summary statistics for

continuous variables cover n, mean, SD, min, median, and max.

For each scheduled post-baseline visit, descriptive statistics for all vital sign parameters will be presented for observed values and change from baseline.

A frequency table will be presented with the number of participants reporting at least one ontreatment abnormality.

#### Laboratory

Laboratory parameters will be presented for each treatment group. Summary statistics for continuous variables will cover n, mean, SD, min, median, and max. Frequency tables will cover number and percentage of participants in the respective category.

For each scheduled post-baseline visit, descriptive statistics for all clinical chemistry and hematology parameters will be presented for observed values and change from baseline.

A frequency table will present number of participants reporting at least one treatment emergent change in laboratory parameters outside predefined criteria.

Elevation in liver parameters for assessment of HL will be reported appropriately if potential cases have been identified during the course of the study.

## Electrocardiogram

ECG parameters will be presented for each treatment group. Summary statistics for continuous variables will cover n, mean, SD, min, median and max. Frequency tables will cover number and percentage of participants in the respective category. The (uncorrected) QT interval will be corrected according to the Fridericia's formula. Parameters to be tabulated are listed in Section 3.1.

For each scheduled post-baseline assessment, descriptive statistics for all ECG parameters will be presented for observed values and change from baseline. Additionally, summaries will be made of all ECG parameters fulfilling potentially clinically significant criteria during the treatment period.

# 9.4.4 Analysis of Pharmacokinetics and Immunogenicity

Immunogenicity results will be analyzed descriptively by summarizing the number and percentage of participants who develop detectable ADAs against cotadutide. The immunogenicity titer, and ADA cross-reactive to GLP-1 and glucagon will be reported for samples confirmed positive for the presence of ADAs. The effect of immunogenicity on PK and safety will be evaluated, if data allow. Sparsely collected plasma concentrations will be descriptively summarized. Any issues considered to impact the PK data (such as, but not limited to participants not receiving complete/full intended cotadutide dose) may result in the

exclusion of concentration data from the PK analysis or exclusion from the PK summaries or descriptive statistics, the reason(s) for exclusion will be documented. The available concentration data for any participants excluded from the PK data summaries or descriptive statistics will be listed. If data are used in the population PK and the exposure-response analyses, the results will be reported in a separate report.

# 9.5 Interim Analyses

Not applicable.

# 9.6 Data Monitoring Committee

An independent DMC will be established to monitor data on an ongoing basis to ensure the safety of participants enrolled in this study and the integrity of the study. The DMC will meet periodically during the study to review the safety data and operate according to the procedures and processes described in full detail in the DMC charter.

For details on the DMC, refer to Appendix A 5.

# 10 SUPPORTING DOCUMENTATION AND OPERATIONAL CONSIDERATIONS

# Appendix A Regulatory, Ethical, and Study Oversight Considerations

# A 1 Regulatory and Ethical Considerations

- This study will be conducted in accordance with the protocol and with the following:
  - Consensus ethical principles derived from international guidelines including the Declaration of Helsinki and Council for International Organizations of Medical Sciences (CIOMS) International Ethical Guidelines.
  - Applicable ICH GCP Guidelines.
  - Applicable laws and regulations.
- The protocol, protocol amendments, ICF, Investigator Brochure, and other relevant documents (eg, advertisements) must be submitted to an IRB/IEC by the investigator and reviewed and approved by the IRB/IEC before the study is initiated.
- Any amendments to the protocol will require IRB/IEC and applicable Regulatory Authority approval before implementation of changes made to the study design, except for changes necessary to eliminate an immediate hazard to study participants.
- AstraZeneca will be responsible for obtaining the required authorizations to conduct the study from the concerned Regulatory Authority. This responsibility may be delegated to a CRO but the accountability remains with AstraZeneca.
- The investigator will be responsible for providing oversight of the conduct of the study at the site and adherence to requirements of 21 CFR, ICH guidelines, the IRB/IEC, European Regulation 536/2014 for clinical studies (if applicable), European Medical Device Regulation 2017/745 for clinical device research (if applicable), and all other applicable local regulations.

#### **Regulatory Reporting Requirements for Serious Adverse Events**

- Prompt notification by the investigator to the sponsor of a SAE is essential so that legal obligations and ethical responsibilities toward the safety of participants and the safety of a study intervention under clinical investigation are met.
- The sponsor has a legal responsibility to notify both the local regulatory authority and other regulatory agencies about the safety of a study intervention under clinical investigation. The sponsor will comply with country-specific regulatory requirements relating to safety reporting to the regulatory authority, IRB/IEC, and investigators.
- For all studies except those utilizing medical devices, investigator safety reports must be prepared for suspected unexpected serious adverse reactions (SUSAR) according to local regulatory requirements and sponsor policy and forwarded to investigators as necessary.
  - European Medical Device Regulation 2017/745 for clinical device research (if applicable), and all other applicable local regulations

 An investigator who receives an investigator safety report describing a SAE or other specific safety information (eg, summary or listing of SAEs) from the sponsor will review and then file it along with the [Investigator's Brochure or state other documents] and will notify the IRB/IEC, if appropriate according to local requirements.

#### **Regulatory Reporting Requirements for Serious Breaches**

- Prompt notification by the investigator to AstraZeneca of any (potential) serious breach of the protocol or regulations is essential so that legal and ethical obligations are met.
  - A 'serious breach' means a breach likely to affect to a significant degree the safety and rights of a participant or the reliability and robustness of the data generated in the clinical study.
- If any (potential) serious breach occurs in the course of the study, investigators or other site personnel will inform the appropriate AstraZeneca representatives immediately after he or she becomes aware of it.
- In certain regions/countries, AstraZeneca has a legal responsibility to notify both the local regulatory authority and other regulatory agencies about such breaches.
  - AstraZeneca will comply with country-specific regulatory requirements relating to serious breach reporting to the regulatory authority, IRB/IEC, and investigators. If EU Clinical Trials Regulation 536/2014 applies, AstraZeneca is required to enter details of serious breaches into the European Medicines Agency CTIS. It is important to note that redacted versions of serious breach reports will be available to the public via CTIS.
- The investigator should have a process in place to ensure that:
  - The site staff or service providers delegated by the investigator/institution are able to identify the occurrence of a (potential) serious breach.
  - A (potential) serious breach is promptly reported to AstraZeneca or delegated party, through the contacts (email address or telephone number) provided by AstraZeneca.

